The micropatch will be placed perpendicularly to the skin surface and the microneedles will be inserted by the application of gentle force to the back of the array (the study team member will apply this gentle pressure with their thumb or use of a hand-held applicator). The pressure will be applied for approximately 10 seconds and then the patch will be removed. The patch will be rotated 45 degrees and the same process will be repeated, in order to create a total of 100 non-overlapping pores. The micropatch treatment will only occur on the first study day.

The following procedure will be used to make the baseline and all following measurements of the 9 identified sites:

Several quick measurements will be made at each site, using noninvasive probes.

- Transepidermal water loss (TEWL) will be measured at each site by placing a small probe on the surface of the skin for approximately 1 - 3 minutes at each site. This measurement will not be repeated after Day 0 procedures.
- The hydration level of the skin will be measured at each site by placing a corneometer probe lightly on the skin; each measurement takes less than 1 minute at each site.
- The redness and color of the skin will be measured at each site by placing a colorimetry probe on skin for less than 1 minute at each site.
- Impedance will be measured using an impedance meter with a series of electrodes. This process takes approximately 2 minutes at each site.

Subjects will be asked to return to the CRU at 24 hour intervals for 4 days (24, 48, 72, and 96 hours) after microneedle insertion. At each of these return visits the baseline measurements will be repeated (excluding TEWL measurements). Occlusive coverings will be removed before measurements are taken, and fresh material will be applied afterwards. Each visit will last approximately 1 1/2 - 2 hours.

Within 2 to 3 days following completion of the study, one of the study team members will follow up with the subject via phone or email to determine if the subject is having any redness or skin irritation at the site of any of the treatments. There is no long-term follow up necessary. The overall time commitment for the subjects is approximately 11 - 14 hours with 5 study days (6 if consent and Day 0 procedures do not occur on same day) over 1 week.

VII.E.7 *Will you attempt to recontact subjects who are lost to follow-up?*

No - those lost to followup will not be recontacted

VII.E.9 *Will subjects be provided any compensation for participating in this study?*

Yes

VII.E.10 *Cash*
No

VII.E.11 *Gift Card*
No

VII.E.12 *Check*
Yes

VII.E.13 *Who will be providing the research compensation check to the subject?*
Accounting Services directly via the e-Voucher system

VII.E.16 *Other*
No

VII.E.19 *Describe the compensation plan including*

- *Compensation amount and type per visit*
- *Total compensation*
- *Pro-rating for early withdrawal from study*

Subjects will receive the following compensation:

Day 1-\$50
Day 2-\$25
Day 3-\$25
Day 4-\$25
Day 5-\$25

Total compensation- \$150

Compensation will be prorated for any subject who does not complete all days of the study. Subjects will only be paid for the study days they complete. Subjects will be paid in one check.

VIII. Risks

VIII.1

What are the risks to subjects including

- emotional or psychological
- financial
- legal or social
- physical?

In general, microneedle treatments are well tolerated. However, the skin could become irritated from the microneedle insertion or from the adhesives (either on the micropatches used to apply the microneedles and make measurements, or the medical tape used to hold the occlusive material in place). There may be mild discomfort, itching, redness, bruising, or hyper-/hypopigmentation at the treatment sites or where adhesives were in contact with the skin. Loss of confidentiality is also a risk.

VIII.2

What have you done to minimize the risks?

- *If applicable to this study ALSO include:*

- *How you (members of your research team at Iowa) will monitor the safety of individual subjects.*
- *Include a description of the availability of medical or psychological resources that subjects might require as a consequence of participating in this research and how referral will occur if necessary (e.g. availability of emergency medical care, psychological counseling, etc.)*

During the consent process the subjects will be counseled about the micropatch. The skin will be cleansed thoroughly with alcohol wipes prior to applying the micropatch (cleaning technique similar to that used for insertion of a typical hypodermic needle). They will also be counseled about the possibility of local skin irritation and redness from the adhesive tape. Subjects will be closely observed during the measurements and during treatment with the micropatch; emergency facilities and staff will be available if necessary. Subjects will be instructed to contact a member of the study team if problems arise at any time during their participation in the study (all pertinent contact information will be provided to the subjects). Approximately 2 - 3 days following study completion, a member of the research team will call or email the subject to follow-up and be sure that no irritation or infection has occurred.

The risk of loss of confidentiality will be minimized by keeping all documents in a locked cabinet that is only accessible to members of the research team. All electronic forms of data will be kept on a secure-server supported by the University of Iowa that allows only members of the research team access.

VIII.3

Does this study have a plan to have an individual or committee review combined data from all subjects on a periodic basis (such as summary or aggregate safety and/or efficacy data)?

No

IX. Benefits

IX.1

What are the direct benefits to the subject (do not include compensation or hypothesized results)?

There are no direct benefits to the subjects.

IX.2

What are the potential benefits to society in terms of knowledge to be gained as a result of this project?

As microneedles have now been commercialized with the introduction of the Fluzone Intradermal vaccine in 2011, it is important to learn how different patient populations respond to microneedle treatment so that this unique drug delivery technique can be developed for other applications. The response of different skin types to microneedle application through a micropatch has not been studied previously, and the knowledge gained from this project will help us to optimize drug delivery systems that are non-invasive and can be used in multiple patient populations.

X. Privacy & Confidentiality

X.1

What are you doing to protect the privacy interests of the subjects?

No direct patient identifiers will be recorded on data collection material. Instead, subjects will be assigned a subject number on study materials. Only the data necessary to answer the research question will be collected, and all consent processes and study procedures will take place in a private location in the Clinical Research Unit.

X.2

Are you collecting the Social Security Number of any subjects for any purpose?

Yes

X.3

Provide the intended usage of SSN:

- To provide compensation to subjects

X.4

How will information/data be collected and stored for this study (check all that apply):

- Paper/hard copy records (hard copy surveys, questionnaires, case report forms, pictures, etc.) - Hard copies will only be transported by members of the research team. Hard copies will be stored in the office of the Clinical Coordinator in C44-P of the ICTS center of UIHC or in the office of the Clinical Coordinator in 558 CPB in a locked filing cabinet only accessible to members of the study team. Upon closure of the study documents will be stored in the office of the Clinical coordinator in 558 CPB or in B105 and B109 ML.
- Electronic records (computer files, electronic databases, etc.) - Electronic results and data (after direct patient identifiers have been removed) will be kept on a password protected shared drive (College of Pharmacy, University of Iowa) that only members of the research team will be able to access.
 - Name - [name]
 - Title - IT Director

- o University Job Classification - Faculty/Staff

X.5 *Do the confidentiality protections indicated above allow only members of the research team to access the data/specimens?*
 Yes

X.7 *Does your study meet the NIH criteria for a [Certificate of Confidentiality](#), or will you be applying for Certificate of Confidentiality?*
 No

XI. Data Analysis

XI.1 *Describe the analysis methods you will use, including, if applicable, the variables you will analyze*

Descriptive statistics will be used for subject demographics. Each subject will serve as their own control, and paired t-tests will determine differences in TEWL (water loss measurements) from baseline to post-microneedle insertion (this is used to determine if the microneedles adequately breached the skin barrier). For the colorimetry and hydration measurements, each daily measurement will be compared to its baseline at that site using paired t-tests. The percent change in TEWL measurements from baseline to post-microneedle application will be calculated and compared between groups.

The impedance data for this study will be analyzed using similar methods as our previous study. The Z-pores impedance value will be calculated, and Student's t-tests will be used to ensure that micropores were adequately created (demonstrated by a significant decrease in impedance from baseline). Next, Z-pores will be calculated from impedance measurements taken over several hours to days following microneedle treatment (depending on the subject group), and then converted to admittance (admittance is the inverse of impedance). The admittance can demonstrate how "open" the micropores are in a very intuitive manner. If a micropore has a maximum admittance, then the micropore is 100% open. Using this information, we will plot admittance vs. time and calculate a rate constant of micropore admittance (k). The rate constant is then used to calculate the half-life of micropore closure, which thus describes a rate of closure in units of time.

XI.2 *Provide the rationale or power analysis to support the number of subjects proposed to complete this study.*

There is no data in any population other than Caucasian individuals to guide a formal power analysis. Our calculation of subject number was based on what is feasible for a pilot study to give enough preliminary data for a power analysis later. We plan to enroll subjects into 2 groups, determined by their BMI. Group 1: BMI <29.9; Group 2: BMI >30. Within each group there will be 80 subjects, divided as follows: 10 African American or Black, 10 Hispanic/Latino, 10 Caucasian/White, 20 Asian, and 10 American Indian/Alaskan Native, 10 Native Hawaiian/Other Pacific Islander, 10 bi-/multiracial. The Asian group contains more individuals because this racial/ethnic category encompasses individuals from a very large geographic area (China, Japan, India, Thailand, Korea, etc.) and therefore more subjects may be necessary to see significant trends. We have selected 180 subjects as the number for enrollment to help account for those who will complete the informed consent form but will be screened out afterwards.

XII. Future Research

XII.1 *Do you wish to keep any information about subjects involved with this research project so that members of the current research team may contact them in the future for your own research projects?*
 Yes

XII.2 *Do you wish to keep any information about subjects involved with this research project so that [other researchers](#) may contact them for future research?*
 No

XII.3 *List the data or information you will keep:*
 Name and contact information.

XII.4 *Does this project involve storing any data, tissues or specimens for future research?*
 No

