VI.1 *How many adult subjects do you expect to consent or enroll for this project?*
180

VI.2 *What is the age of the youngest adult subject?*
18.0

VI.3 *What is the age of the oldest adult subject?*
50.0

VI.4 *What is the percentage of adult male subjects?*
50

VI.5 *What is the percentage of adult female subjects?*
50

VI.6 *How many minor subjects do you expect to consent or enroll for this project?*
0

VI.13 *Describe EACH of your subject populations*

- *Include description of any control group(s)*
- *Specify the Inclusion/Exclusion criteria for EACH group*

Approximately 180 subjects aged 18 - 50 will be consented for the study. Target enrollment is 160 subjects, and we anticipate that there will be subjects who will sign consent but not complete the study.

Inclusion criteria: Subjects will be healthy men and women between 18 - 50 years of age who identify as African American or Black, Asian, Hispanic or Latino, American Indian/Alaska Native, Native Hawaiian/Other Pacific Islander, Caucasian/White, bi-/multiracial.

Exclusion criteria: Unable to give consent; severe general allergies requiring chronic treatment with steroids or antihistamines; previous adverse reaction to microneedle insertion; known allergy or adverse reaction to medical tape/adhesive or aloe vera; any inflammatory diseases of the skin; psoriasis, atopic dermatitis, and blistering skin disorders; diseases associated with altered immune function (including but not limited to: rheumatoid arthritis, diabetes, lupus, HIV/AIDS); any subjects taking medication that impairs the immune system (including but not limited to corticosteroids, TNF inhibitors, monoclonal antibodies, chemotherapy agents); any current malignancy or history of malignancy present at the treatment site; eczema or scaling present at the treatment site; any current inflammation or irritation present at the treatment site (including but not limited to: rash, inflammation, erythema, edema, blisters). Uncontrolled mental illness that would, in the opinion of the physician, affect the subject's ability to understand or reliably participate in the study will also be excluded.

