After a subject consents to be in the study, baseline demographic data will be collected for each subject including age, sex, height, weight, and Fitzpatrick skin type (determined by a member of the study team); information regarding current medical conditions will also be collected. Specifically, the subject's approximate duration of each condition, what treatments the subject has received, and approximate severity of the conditions will be collected, as well as a current medication list. All of this information will be collected directly from the subject and the subject's medical record will not be reviewed/abstracted for research data. After completing the questionnaire a member of the research team will determine if the subject is eligible to continue participating in the study. Subjects will be screened out after this process if their answers to screening questions meet the exclusionary criteria. Consent and screening procedures will require approximately 1 hour.

On the first day of study procedures (Day 0), which may occur on the same day as the consenting process, subjects will first be asked to sit quietly in the CRU for 30 minutes before any study procedures are started, in order for their skin to acclimate to the room temperature and humidity. Nine sites will be identified on the upper arm and marked with a pen. At all marked sites baseline measurements of hydration, colorimetry, trans-epidermal water loss, and impedance will be measured at each site, using noninvasive flat probes (described below). The probes are attached to a computer that calculates measurement units. Three sites will receive the micropatch treatment (described below), and after treatment the trans-epidermal water loss and impedance measurements are repeated and the sites will be covered by blank occlusive material secured to the skin with medical tape. Three of the sites will receive no micropatch treatment but will be covered with occlusive material. Three of the sites will serve as controls and will receive no treatment and they will remain uncovered. Study procedures on this first day (Day 0) will require approximately 2 - 3 hours. Hair may be clipped (but not shaved) at the identified sites prior to start of the study procedures, if necessary.

The following procedure will be used to apply the micropatch for each subject:

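### A subject treated on Day 0 who stops attending is not clearly covered by the 2 to 3 day skin check, and VII.E.7 rules out recontact without a safety exception

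*Combined protocol and SAP*

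**What the plan says.** Four parts of the combined protocol and SAP bear on this.

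- **VII.E.7**, on whether subjects lost to follow-up will be recontacted: "No - those lost to followup will not be recontacted". No exception is stated.
- **VII.E.6**, on procedures, times the team's phone or email enquiry about redness or irritation as follows: "Within 2 to 3 days following completion of the study".
- **VIII.2** lists the same contact among the steps that minimize risk. It is again placed about 2 to 3 days after study completion, when "a member of the research team will call or email the subject to follow-up and be sure that no irritation or infection has occurred".
- **VII.E.19**, on payment, foresees people who stop early: "Compensation will be prorated for any subject who does not complete all days of the study".

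VII.E.6 also fixes the exposure. All micropatch treatment takes place on Day 0, the treated sites are then covered with occlusive material, and the covering is renewed at each return visit at 24, 48, 72 and 96 hours. Subjects have a route of their own to the team: VIII.2 tells them to make contact if problems arise while they are taking part, and "all pertinent contact information will be provided to the subjects".

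**The concern.** The contact is offered as a safeguard, but the text ties it to an event, completion, that an early stopper may never reach. The neighbouring item then says that people who are lost will not be pursued. Followed as written, the two statements can leave a treated subject with no check that the team initiates after the last attended visit.

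Those affected would be the subjects with the fewest observed visits. Someone who leaves after Day 0 goes home with three treated sites under occlusion and is not seen again. Section I.6 puts micropore closure under occlusion at roughly 48 to 72 hours in young healthy people, so a subject last seen on Day 0 or at 24 hours was last examined before closure is expected. VII.E.6 and VIII.2 do not say what that subject should do about the covering.

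What is at stake is a small amount of safety oversight. A secondary matter is that a contact after a missed visit might bring some subjects back for later impedance readings, from which XI.1 derives the closure rate constant.

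**Working it through.** The plan gives no figure to reproduce, and the point depends on no error rate, effect size or sample size. The check compares the sections and then counts.

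**Step 1: who is exposed.** Treatment is confined to Day 0 (VII.E.6). Anyone who attends Day 0 procedures and later stops has been treated.

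**Step 2: what triggers the contact.** Both descriptions (VII.E.6 and VIII.2) start the clock at completion of the study. Neither mentions a subject who stops early.

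**Step 3: what completion means.** The plan does not define it. VII.E.19 speaks of completing all days, and pays pro rata those who do not. That is a payment rule and does not settle who gets the call, but it shows that early stopping after treatment is contemplated.

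**Step 4: what happens to someone who stops attending.** VII.E.7 excludes recontact of those lost to follow-up, a term that is also undefined. If no one tries to reach an absent subject, a person who has merely missed visits cannot be told apart from one who is lost.

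**Step 5: count the team checks after Day 0.** A check here is a return visit or the planned contact.

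Checks clearly assured now = return visits attended + 1 if the subject completes. For a completer, 4 + 1 = 5.

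With the fix, checks attended or attempted = return visits attended + 1 for every treated subject.

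Contact window after insertion = time of last attended visit + 48 to 72 h.

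| Last attended visit | Return visits attended | Clearly assured now | With the fix (contact attempted) | Contact window after insertion |
|---|---|---|---|---|
| Day 0 | 0 | 0 | 0 + 1 = 1 | 48–72 h |
| 24 h | 1 | 1 | 1 + 1 = 2 | 24 + 48 to 24 + 72 = 72–96 h |
| 48 h | 2 | 2 | 2 + 1 = 3 | 96–120 h |
| 72 h | 3 | 3 | 3 + 1 = 4 | 120–144 h |
| 96 h (completer) | 4 | 4 + 1 = 5 | 5 | 144–168 h |

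The fix adds one attempted check per early stopper. For a Day 0 stopper, it falls in the period when I.6 expects closure in young healthy skin.

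**Step 6: how many subjects.** This cannot be computed. The plan states no rate of stopping after treatment.

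**The case against.** The strongest reply is that the plan excludes no one and is only loosely worded. Completion can be read subject by subject, as the end of that person's own participation, since the call goes to the individual. Loss to follow-up often means that contact has already failed, so one missed visit would not qualify. On that reading an early stopper gets the call, and VII.E.7 only rules out chasing people who cannot be reached. This reading is possible, and for that reason the claim is limited to subjects being not clearly covered. A reader might go further and infer that the plan deliberately denies early stoppers a safety check, or that its sections contradict each other. With both terms undefined, the text does not establish either. But no passage extends the check to early stoppers, and VII.E.7 points the other way.

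The second reply is that little is at risk. VIII.1 lists minor local effects: "There may be mild discomfort, itching, redness, bruising, or hyper-/hypopigmentation at the treatment sites". Subjects are counseled about irritation and hold the team's contact details. Someone who has stopped attending may also not answer a call. All of this stands, and it limits the benefit. It does not explain why a safeguard that VIII.2 relies on should have an unclear population.

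The third reply is that the consent document, which is not in the copy reviewed, may give withdrawal or aftercare instructions. That is also fair, so the point is confined to VII.E.6, VII.E.7 and VIII.2.

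Two further inferences should be resisted.

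- VI.13 says "we anticipate that there will be subjects who will sign consent but not complete the study", and the margin between 180 consented and 160 targeted might be taken as an expected dropout rate. XI.2 attributes that margin to people screened out after consent. VII.E.6 places screening before the Day 0 procedures, so those people are never treated.
- It might be inferred that the recontact rule materially weakens the group comparison. A Day 0 stopper does leave only one post-treatment time and so no rate constant. But with no loss rate and no reminder success rate in the plan, any figure for lost precision would rest on invented inputs.

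**Conclusion.** The point holds as a modest safety gap; it is not a statistical error. As written, a subject treated on Day 0 who stops attending is not clearly covered by any team-initiated skin check after the last attended visit, and depends on reporting problems unprompted. A subject who formally withdraws may or may not be covered. The size is one attempted check per early stopper, which matters most for someone last seen on Day 0, who is otherwise assured of none. The number of such subjects is unknown.

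The conclusion assumes that the consent document does not already extend the contact to early stoppers. It also assumes that VII.E.7 would be applied literally. Any benefit for retention of impedance data is secondary and is left unquantified.

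**What to change.** In VII.E.6 and VIII.2, state that the 2 to 3 day phone or email contact about irritation and infection will be attempted for every subject who received a micropatch, timed from that subject's last attended visit, unless the subject declines contact. Amend VII.E.7 so that it permits this safety contact. The same call or email may also serve as a reminder after a missed visit.

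The cost is a form amendment and one or two calls or emails per early stopper. The procedure already exists for completers, so the team needs no new measurement and no contact details beyond those that the planned check already requires.

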A number of drug exposure and response factors can be significantly altered in racial subpopulations; these can include pharmacokinetic dose-proportionality, therapeutic index, bioavailability, steepness of the relationship between dose and response, and genetic polymorphisms in metabolism pathways. Whether or not these differences have an effect when a drug is administered via the skin, specifically with microneedles, is unknown. The most obvious skin difference between individuals of varying race is pigmentation. A number of other significant skin differences exist that cannot be visually observed, including epidermal thickness and reactivity. Mean electrical resistance is significantly higher in Black vs. Caucasian individuals, suggesting that the stratum corneum (outer epidermal layer) is thicker or more cohesive, or both. Decreased transdermal penetration of pharmaceuticals has been observed in Black persons (relative to Caucasian). The barrier of darkly pigmented skin is generally more resistant and recovers more quickly to insult than skin of lighter pigmentation. The epidermis is thicker in Korean and Black vs. Caucasian skin. Asian, Caucasian, and Black individuals also have dissimilar levels of skin reactivity. Additional variables that differ between skin of diverse race/ethnicity include transepidermal water loss, hydration, and sebum content. All of these factors could cause clinically relevant differences in micropore healing and drug exposure.

In this study we will measure hydration to characterize the epidermal properties of individuals of different self-identified races. Measurements of water loss and movement of electrical current (impedance measurements) will be used to evaluate the rate of micropore closure. The skin serves as the primary barrier to loss of water from the body, and disruptions of skin barrier function (as seen with microneedle insertion) result in a significant increase in water loss. The skin also serves as a barrier to the movement of electrical current, and a breach of the skin barrier leads to significant decreases in the impedance measurements. Therefore, both of these serve as surrogate markers of barrier function and can be measured noninvasively.

I.7 *Literature cited / references (if attaching a grant or protocol enter N/A).*
N/A

II. Research Team

II.1 *Principal Investigator*

Name	E-mail	College
[name]	[contact]	College of Pharmacy

II.2 *Team Members*

UI Team Members

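### Hydration and colour are tested only against each site's own baseline; with no contrast between site types, the plan cannot isolate the micropatch's effect on these two supporting measures (minor, cheap to improve)

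*Combined protocol and SAP*

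**What the plan says.** The only test stated for these two measures is in XI.1: "For the colorimetry and hydration measurements, each daily measurement will be compared to its baseline at that site using paired t-tests".

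VII.E.6 describes nine sites per subject, in three conditions of three sites each. For the treated sites, "after treatment the trans-epidermal water loss and impedance measurements are repeated and the sites will be covered by blank occlusive material". For the second set, "Three of the sites will receive no micropatch treatment but will be covered with occlusive material". The third set is untreated and stays uncovered; I.4 describes these as controls. Hydration and colour are read at all nine sites on Day 0 before any treatment. They are read again at 24, 48, 72 and 96 hours once the coverings are off; the procedure is introduced with "The following procedure will be used to make the baseline and all following measurements of the 9 identified sites".

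I.6 gives hydration a descriptive role: "In this study we will measure hydration to characterize the epidermal properties of individuals of different self-identified races". It rests micropore closure on water loss and impedance. On colour, VII.E.6 says "The redness and color of the skin will be measured at each site by placing a colorimetry probe on skin".

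**The concern.** A treated site is both punctured and covered, and its hydration and colour are not read between insertion and covering. Its change from baseline at 24 hours or later therefore mixes three things: the micropatch, the covering and tape, and the passage of days. The documents name two of these as sources of what the colorimeter reads. VIII.1 says "There may be mild discomfort, itching, redness, bruising, or hyper-/hypopigmentation at the treatment sites or where adhesives were in contact with the skin", and VIII.2 says of the subjects "They will also be counseled about the possibility of local skin irritation and redness from the adhesive tape".

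The design contains the sites that could separate these sources, but the analysis section does not contrast them. A reader who wants to know whether the micropatch changed hydration or redness would have to set a significant result at treated sites beside a non-significant one at occlusion-only sites. A difference in significance is not a test of the difference, and it gives no estimate or interval. What is at stake is the interpretation of two supporting measures, not the time-to-repair question in I.5.

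**Working it through.** **Step 1: is a contrast stated elsewhere?** The candidates do not supply one.
- The own-control sentence in XI.1 is completed by water loss before versus after insertion.
- The between-groups comparison in XI.1 is of percent change in water loss.
- The methods carried over from a previous study are for impedance.
- VII.B.11 answers No to a separate written protocol.

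**Step 2: what each change contains.** Write M for the micropatch effect under occlusion, C for covering and tape, and T for day effects.
- Treated: M + C + T
- Occlusion-only: C + T
- Uncovered: T

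Treated minus occlusion-only gives M. Occlusion-only minus uncovered gives C. A within-site test at a treated site can only address the sum M + C + T.

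**Step 3: how often could comparison by eye mislead?** The documents give no SDs, correlations or alpha, so this is an illustration.
- From XI.2: n = 10 per race-by-BMI cell (20 for Asian), 80 per BMI group, 160 in all.
- Assumed: two-sided 5% paired t-tests; M = 0; a shift d (in SDs of a single-site change) equal at treated and occlusion-only sites; between-site correlation of change r.

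At d = 0.5, the noncentral t gives each within-site test a rejection probability of 0.293 at n=10 and 0.565 at n=20. This is power to detect a real change, not an error rate.

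The misleading pattern is treated significant, occlusion-only not. At r = 0 it is power × (1 − power): 0.293 × 0.707 = 0.207 at n=10, and 0.565 × 0.435 = 0.246 at n=20. Simulation with one site of each type gives:

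| d | n | r=0 | r=0.25 | r=0.5 | r=0.8 |
|---|---|---|---|---|---|
| 0.25 | 10 | 9.8% | 8.9% | 7.7% | 5.3% |
| 0.25 | 20 | 15.1% | 13.4% | 11.1% | 7.1% |
| 0.5 | 10 | 20.7% | 18.1% | 15.0% | 9.6% |
| 0.5 | 20 | 24.6% | 21.0% | 16.9% | 10.5% |
| 1.0 | 10 | 15.9% | 14.1% | 11.7% | 7.6% |
| 1.0 | 20 | 1.1% | 1.1% | 1.0% | 0.7% |

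XI.1 states neither the testing unit nor whether replicate sites are averaged, so two variants matter.
- *Pooled subjects, single sites.* At d = 0.5 the pattern occurs in about 0.5–0.7% of cases at n=80 and about 0% at n=160. At d = 0.25 it remains: at r = 0, 0.598 × 0.402 = 0.240 at n=80 and 0.882 × 0.118 = 0.104 at n=160, falling to about 10% and 5% at r = 0.8.
- *Three-site means, d = 0.5.* About 6–22% at n=10 and 4–10% at n=20.

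The direct contrast of changes rejects in about 5% throughout. That holds by construction, because the shift is set equal at both site types.

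**Step 4: precision of the contrast.** In SDs of a single-site change, averaging three sites per condition:
- contrast SD = √(2(1−r)/3)
- SD of one three-site mean change = √(r + (1−r)/3)
- effect detectable with 80% power = 0.996 × contrast SD at n=10, and 0.660 × contrast SD at n=20

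| r | contrast SD | three-site-mean SD | ratio | detectable, n=10 | detectable, n=20 |
|---|---|---|---|---|---|
| 0 | 0.816 | 0.577 | 1.41 | 0.81 | 0.54 |
| 0.25 | 0.707 | 0.707 | 1.00 | 0.70 | 0.47 |
| 0.5 | 0.577 | 0.816 | 0.71 | 0.58 | 0.38 |
| 0.8 | 0.365 | 0.931 | 0.39 | 0.36 | 0.24 |

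**The case against.** The strongest reply is that no planned inference is wrong. The within-site tests answer the question they pose, the aim in I.5 concerns repair time across racial and ethnic groups, and a micropatch effect on hydration or redness is not a stated aim. The control sites are not ignored either: the XI.1 sentence covers every measured site, so their changes will appear beside those of the treated sites. All readings are kept, so the contrast could be run later in what XI.2 calls a pilot. This stands, and it is why the point is minor. It does not remove the gap: results side by side are not a contrast, and one specified in advance is worth more than one chosen after the data are seen.

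The illustration is also open to challenge, because the 10–25% figures need cell-level, single-site tests and an assumed 0.5 SD shift. That stands too. Pooling removes the problem at that shift, though not at 0.25 SD.

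A reader might infer more: that the investigators will credit treated-site changes to the micropatch, or that the closure results are confounded. The documents support neither. Nowhere do they say these changes will be attributed to the micropatch. Closure rests on other measurements, and the Day 0 checks of pore creation use water loss and impedance repeated before the sites are covered.

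**Conclusion.** The point holds as a minor, cheaply remedied omission on two supporting measures. As written, XI.1 will show which sites changed from their own baseline. It will give no estimate or test that separates the micropatch from covering, tape and day effects, although the readings needed for one are collected at every return visit. That conclusion follows from the text and needs no assumed numbers.

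Its practical size cannot be fixed from the documents. Depending on the shift, the correlation, the testing unit and the averaging of sites, the misleading pattern ranges from about 0% to about 25% in the settings examined.

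**What to change.** In XI.1, average the three sites per condition within each subject. For hydration and each colour index, at 24, 48, 72 and 96 hours, estimate with a 95% confidence interval the within-subject difference in change from baseline for:
- (a) treated minus occlusion-only, the micropatch effect under occlusion;
- (b) occlusion-only minus uncovered, the covering and tape effect.

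Keep the within-site tests as descriptive, and state whether the analysis is by cell, by BMI group or over all subjects.

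The change is to wording only; no visit or reading is added. It has three costs.
- It adds at least 16 comparisons (2 contrasts × 4 times × hydration and one colour index), and more with further indices or by cell. Label them exploratory and read them through estimates and intervals.
- Differencing adds noise relative to a three-site mean change when the between-site correlation of change is below 0.25 (1.41 times the SD at zero correlation).
- The micropatch effect is estimated under occlusion only, because no treated site is left uncovered.
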